### End of study procedures

1. At the end of the 12 week study, participants will be notified the group to which they were assigned (low amplification or full amplification). Participants in the low amplification group will meet with the study audiologist to have their hearing aids set to full gain as per standard clinical practice. All participants will be allowed to keep their hearing aids and will have clinical follow up visits scheduled in the Columbia Otology clinic as per routine practice. Patients will use their insurance or otherwise cover the costs of their clinical audiologic care as they normally would outside the context of a research study. However, the study will cover one post-protocol audiology visit for participants in the low-amplification group in order to ensure the devices are working correctly and to answer questions the patient may have about their newly working devices.
2. Patients will also receive the typical 3 months post-protocol open treatment in the CAAM. Depending on their clinical status, options to continue, augment, switch, or begin the study antidepressant medication will be discussed with patients.

### COVID-19 Phase 1 Re-Opening:

I attest to follow the COVID-19 Safety Guidelines for Columbia Psychiatry and NYSPI Re-Entry outlined in the NYSPI Director's June 1st memo, which include but are not limited to:

- Infection Control/PPE – Guidelines
- Research participants will only come on-site if absolutely necessary for study procedures.
- No volunteers/externs on-site during Stage 1.
- Clinical research teams will screen their participants for COVID symptoms (night before and day of onsite visit, documenting this in the chart), and escort them in and out of the building.
- COVID/COVID-like symptoms in participants will be reported to the IRB via PRISM as an SAE.

### Baseline/Week 0:

This visit will be completed in two components, one in-person and one virtual. When a participant comes in to complete the in-person portion of the evaluation, they will also complete the baseline neuropsychological (NIH Toolbox DCCST and Flanker, RBANS-H) and physical (SPPB, Gait Speed) measures, which must be completed in-person with a research staff member, as well as the physical examination. Participants will be asked COVID-19 screening questions before entering the building on the day of the in-person visit. Institute Safety guidelines for social distancing during visits and appropriate sanitation plans will be implemented and maintained. The audiology appointment will remain an in-person visit. The remainder of the

Baseline/Week 0 visit will be conducted virtually with both a research staff member and study clinician. If necessary, the Baseline/Week 0 virtual visit may become an in-person visit, at the discretion of the clinician.

#### Week 2-Week 9 Visits:

Week 2, 4, 6, and 9 psychiatric follow-up study visits will be completed virtually. If necessary, any virtual visit may become an in-person visit, at the discretion of the study clinician. Audiology appointments will remain as in-person visits.

#### Week 12:

This visit will be completed in two components, one in-person and one virtual. During the in-person portion, the participant will complete the endpoint neuropsychological (NIH Toolbox DCCST and Flanker, RBANS-H) and physical (SPPB, Gait Speed) measures, which must be completed in-person with a research staff member. The remainder of the Week 12 visit will be conducted virtually with both a research staff member and study clinician. If necessary, the Week 12 virtual visit may become an in-person visit, at the discretion of the clinician. The audiology appointment will remain an in-person visit.

#### Open Treatment:

The three-month open treatment procedures will be conducted virtually, per the protocol, with monthly check-in visits occurring virtually.

#### MRI Scans:

Scanning procedures will continue as usually conducted per the protocol once the NYSPI MRI suite re-opens for scanning. COVID-19 screeners will be completed as per suite guidelines. If a patient is scanning-eligible, a research staff member will schedule the Baseline MRI scan as close to the evaluation date as possible. The NYSPI MRI Suite may have limited availability due to the backlog generated by the COVID-19 pandemic. Safety procedures to ensure social distancing and minimal physical contact will be strictly followed. Compensation for these scans will be provided by sending participants an e-gift card, physical gift card, or check.

Patients will be offered paid transportation (i.e. Uber car service) to clinic for in-person visits, subject to a \$50 limit each way per week.

You can upload charts or diagrams if any

## Criteria for Early Discontinuation

### Criteria for Early Discontinuation

The risk of receiving low amplification hearing aids, no antidepressant medication, or non-response to antidepressant medication during the study period is addressed by having close clinical follow up of study subjects and stringent withdrawal criteria. These criteria are (1) participant withdraws his or her consent; (2) significant clinical worsening in the judgment of the study clinician; (3) a CGI-Improvement rating of 6 (worse) or 7 (much worse) for 2 consecutive visits; or (4) development of significant side effects or an adverse event. Any subjects meeting any of these criteria will be withdrawn from the study and treated

clinically. Furthermore, subjects may be withdrawn if they repeatedly miss scheduled appointments or clinical worsening necessitates more intensive treatment.

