## Specific Aims and Hypotheses

### Specific Aims and Hypotheses

**Aim 1:** To investigate baseline relationships between ARHL, CCN circuit measures, and neuropsychiatric measures.

**Hypothesis 1:** More severe ARHL (higher thresholds on pure tone audiometry) will be associated with diminished connectivity and activation within the CCN, which themselves will be associated with poorer executive functioning and increased depressive symptoms.

**Aim 2:** To investigate whether augmentation of standard antidepressant medication treatment with hearing assistive devices is useful for the treatment of comorbid ARHL and LLD.

**Hypothesis 2:** AD + full amplification hearing aids will result in greater depressive symptom improvement (change on Hamilton Rating Scale for Depression [HRSD]) and higher response rates (proportion with Clinical Global Impressions—Improvement [CGI] score of 1 or 2 at endpoint), improved executive functioning, and increased pre-post CCN connectivity and activation compared to AD + low amplification hearing aids.

**Exploratory aims:** To explore the influence of hearing aid compliance (as measured by objective device usage logs) and change in social functioning (as measured by the Social Adjustment Scale—Self Report version [SAS-SR]) on pre-post change in depressive symptoms and executive functioning. We will also attempt to identify pre-treatment participant expectations related to hearing aids as well as participant-identified factors that influence hearing aid use and perceived effectiveness.

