3. Hearing aids will be the latest Audeo B-R 90 devices manufactured by Phonak. Low amplification and full amplification hearing aids will be identical in appearance, battery use, and data logging capability. Low amplification hearing aids will be programmed to prescription for a flat 30dB hearing loss, which will result in a small but noticeable volume increase without substantively improving subject's ability to discriminate speech, which we believe is important for the hearing aids' effect on depressive symptoms. Full amplification hearing aids will have their gain determined by audiometric profile as per standard clinical practice. Real ear measures will be performed to verify fitting, education and counseling will be provided regarding the use of the hearing aid, and subjects will be informed that a minimum of 8 hours/day hearing aid usage is required to stay in the study. To assess compliance with hearing aids, we will measure usage rates (hours/day) using data log technology built into the hearing aids (69-70) Subjects will also sign a hearing aid agreement which includes the provision that if the subject does not complete the 12-week study they must return both hearing aids. If the subject does not complete the 12-week study and would like to keep the hearing aids, he/she can buy the hearing aids at market cost (\$5,300). If a subject does not return the hearing aid, he/she will be charged at market cost for the hearing aid (\$5,300) to the CUMC/Audiology Department. Furthermore, if the subject does not wear the hearing aids for at least 8 hours a day this will disqualify him/her from the study and he/she will have to return all devices. However, if during the study period the subject breaks or loses the hearing aids, we will provide them a new device at no cost to the subject. .

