#### Antidepressant medication

1. Following baseline screening, subjects who choose to start a study medication will receive escitalopram 10mg per day or duloxetine 30mg per day. We opted to allow two potential medication choices so that study participation could be offered to individuals who had previously taken one medication and either not responded or not tolerated it. We selected escitalopram and duloxetine based on established efficacy in

MDD, favorable side effect profiles, minimal drug-drug interactions, and cost effectiveness (i.e., available as generics) (67-68).

2. If the best history-taking efforts of study staff (including patient interview, pharmacy records, or other medical records) indicate that a participant has not responded to or has not tolerated escitalopram or duloxetine, then we will offer an alternative SSRI, SNRI, or bupropion based upon our clinical assessment of the best option given the participant's other medications, medical health, and symptom profile. Similarly, if the patient either fails or is unable to tolerate both of the study medications during the study, they will be initiated on another medication that is clinically indicated. If this is the case, the subject receiving non-study AD medication will be responsible for the cost of the medication co-pay and will pick up the prescriptions from their pharmacy.

3. After 4 weeks if subjects do not meet remission criteria ( $HRSD \leq 10$ ), the dose of study medication will be increased to escitalopram 20mg or duloxetine 60mg for the remaining 8 weeks of the study. Similarly, the dose of the non-study antidepressant medication will be increased under the guidance of the study clinician. Subjects unable to tolerate an increased dose will have their medication reduced to the previously tolerated dose. If a study subject wishes to change antidepressant medication at any point during the study period they may do so under the guidance of the study clinician.

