## Risks/Discomforts/Inconveniences

Risks that could be encountered during the study period

1. Interview, emergencies, and possible suicidal ideation: Subjects may experience discomfort during the clinical interview and evaluations when discussing symptoms and current life events. The study coordinators are experienced and skilled in interviewing depressed subjects. Half-way through the initial assessment, the coordinator will ask the subject if they would like to take a break, and this will be provided if desired. A study clinician will be available during all aspects of the assessment if there are any questions or problems. In addition, should the subject express suicidal ideation at any time during the interview, the study clinician will be contacted immediately to assess the subject and to determine the appropriate course of action. Options for addressing suicidal ideation will include contacting the individual's mental health caregiver, referring for urgent (same day) evaluation and treatment in an outpatient clinic, or emergency room evaluation and hospitalization. Similar practices will be used for other emergencies, including but not limited to psychosis, homicidal or violent thoughts, or an acute change in a subject's physical status.

2. Antidepressant Side Effects: Side effects will be assessed at each planned visit and if needed through additional or unscheduled contacts. We will attempt to minimize side effects by slow dosage titration and allowance for dose reduction if needed. We will withdraw subjects from the study if they cannot tolerate the lowest dose of escitalopram or duloxetine. Side effects of these medications include somnolence, diarrhea, nausea, impaired ejaculation, impotence, dry mouth, tremor, and sweating. Escitalopram and duloxetine have black box warnings regarding an increased risk for suicidal thinking and behavior in adolescents and young adults (less than 24 years old) given the drug. Both drugs are of unknown risk to a fetus. Since the proposed study will enroll subjects aged 60-90 years, these particular risks are not expected to be applicable. Regardless, all subjects will be asked to tell their doctors immediately if they experience suicidal thoughts, and menopausal status and date of last menstrual period will be documented in all female participants.

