Subjects may be prescribed alternative medications (SSRI, SNRI, or bupropion) in the event they are judged to have failed or not tolerated escitalopram and duloxetine. As a class, SSRIs can be associated with somnolence, diarrhea, nausea, impaired ejaculation, impotence, dry mouth, tremor, and sweating, in addition to low risk of increased gastrointestinal bleeding in older adults. SNRIs as a class may be associated with these same risks, in addition to the risk of mildly elevated blood pressure at the upper dosage ranges. The most frequent (occurs in more than 25% of people) side effects of bupropion include

agitation, dry mouth, and headache. Common side effects (occurs in 1-25% of people) include excessive sweating, dizziness, tremor, constipation, nausea, decreased appetite, weight loss, rash, heart pounding, high blood pressure, unsteadiness when walking, confusion, anxiety, increased urination, and difficulty sleeping. Increased risk of seizures occurs in patients taking 400mgs or more.

3. Delay in Initiation of Hearing Treatment: A risk to subjects in this study is the potential delay in receiving effective treatment for their hearing loss. N=20 subjects will receive hearing aids that are not fully tuned such that they improve hearing. Mitigating this risk are the facts that all subjects will be offered an active treatment for depression (i.e., antidepressant medication), and all subjects will be aware that they will receive functioning hearing aids for their hearing loss at the end of the study.

4. Gait speed assessment: During the physical performance assessments, patients may feel unsteady and as such their risk of falls may increase. To mitigate these risks, patients are accompanied by research coordinators and/or doctors during each of the performance-based assessments (including the gait assessment, balance test, and chair stand, the latter two components of the Short Physical Performance Battery). Coordinators walk slightly behind and alongside the patients during the gait assessment, providing support for the patients should they become unsteady during the procedure.

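### Withdrawal for worsening or side effects ends outcome assessment, and the Week 12 analysis makes no provision for those participants

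*Protocol*

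**What the plan says.** **Withdrawal.** The protocol's Criteria for Early Discontinuation list four triggers: (1) withdrawn consent; (2) significant clinical worsening as judged by the study clinician; (3) CGI-Improvement of 6 or 7 at two visits in a row; (4) "development of significant side effects or an adverse event". The consequence is mandatory: "Any subjects meeting any of these criteria will be withdrawn from the study and treated" clinically.

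**Tolerability.** Three further statements apply.
- Antidepressant medication, on a raised dose: "Subjects unable to tolerate an increased dose will have their medication reduced to the previously tolerated dose".
- Antidepressant medication, on both drugs: if participants fail or are "unable to tolerate both of the study medications during the study, they will be initiated on another medication that is clinically indicated". The Risks/Discomforts/Inconveniences section agrees, allowing alternative drugs "in the event they are judged to have failed or not tolerated escitalopram and duloxetine".
- The same Risks section, under antidepressant side effects: "We will withdraw subjects from the study if they cannot tolerate the lowest dose of escitalopram or duloxetine".

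**Devices.** Under Hearing aid procedures, the participant agreement provides that "if the subject does not complete the 12-week study they must return both hearing aids".

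**Outcomes and analysis.** Hypothesis 2 defines response as a CGI-Improvement "score of 1 or 2 at endpoint". The Overview schedules depression visits at Weeks 2, 4, 6, 9 and 12. The SAP's Data Analysis section fits an ANCOVA to Week 0 to Week 12 change, with baseline, group, age and education as predictors. It says the model covers all participants, but not what happens when the Week 12 value is absent.

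**The concern.** For criteria 2 to 4, stopping treatment and leaving the study are one act. With no Week 12 rating, the participant has no outcome in the SAP's model, even if several interim HRSD ratings exist.

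The loss is selective. Criteria 2 and 3 remove people because their depression worsened. Criterion 3 does so on the scale that defines response, so those removed are recorded non-responders. If the hearing aids affect mood, as the trial hypothesises, losses under criteria 2 and 3 could differ between arms, and a comparison of those remaining would no longer be the randomised comparison. Criterion 4 adds loss tied to tolerability.

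The tolerability rules raise a smaller, separate problem. Whether a participant who tolerates neither study drug stays in, and so contributes an endpoint, depends on which section the clinician follows.

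**Working it through.** **1. The plan's own allowance.** Description of Subject Population gives 40 enrolled for 32 completers: 40 − 32 = 8 losses, 8/40 = 20%, and 32/(1 − 0.20) = 40. This covers loss from all causes. Neither document gives an expected number for criteria 2 to 4 or a split by arm.

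**2. Is anything collected after withdrawal?** Overview, Study Assessments, Hearing aid procedures, End of study procedures, the Week 12 and Open Treatment paragraphs, and the discontinuation criteria describe no early-termination visit and no outcome rating after withdrawal. The three-month open treatment is clinical care and names no outcome measure.

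**3. The tolerability rules side by side.**

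| Situation | Antidepressant medication | Risks section | Criterion 4 |
|---|---|---|---|
| Raised dose not tolerated | Reduce, stay in | Dose reduction allowed | Unclear |
| Neither study drug tolerated | Switch, stay in | Withdraw if lowest dose not tolerated; elsewhere switch | Unclear |

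The first row is consistent apart from criterion 4. The second row is a firm conflict, and the Risks section contradicts itself there. Criterion 4 may add to it, because the protocol sets no threshold for a significant side effect and the adverse-event limb can be read as unqualified.

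**4. Precision.** The ANCOVA has five parameters (intercept, group, baseline, age, education), so residual df = n − 5. The 95% half-width for the group effect, in residual SDs and ignoring chance covariate imbalance, is t(0.975, n − 5) × √(1/n₁ + 1/n₂).
- 20 + 20: 2.030 × 0.3162 = 0.642
- 20 + 19: 2.032 × 0.3204 = 0.651
- 19 + 19: 2.035 × 0.3244 = 0.660
- 16 + 16 (the planned completers): 2.052 × 0.3536 = 0.725

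Each lost participant costs little precision, so selection is the issue.

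**5. Selection (illustration; d and G are assumptions).** Let p be the share withdrawn in an arm and G how much worse those withdrawn would have scored at Week 12 than completers in their arm. The full-arm mean is the completer mean + pG. With the same G in both arms, the completers-only difference is off by (p₁ − p₂)G. With 20 per arm (the protocol assigns 20 to low amplification, leaving 20 of 40) and d excess withdrawals in one arm, this is (d/20)G.
- d = 0: 0
- d = 1, G = 0.5: 0.025
- d = 2, G = 1.0: 0.10
- d = 4, G = 1.0: 0.20

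The largest value is 0.20/0.642 = 31% of the half-width at 20 + 20, or 0.20/0.725 = 28% at 16 + 16.

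**6. Response (assumed counts).** If 8 of 20 in an arm respond (40%) and 4 non-responders are withdrawn, completers show 8/16 (50%).

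**The case against.** **Criterion 4 is not the main source of bias.** A reader might infer that any adverse event forces withdrawal and that the protocol has three incompatible tolerability rules. The documents do not establish that. A significant side effect can reasonably mean something worse than the intolerance handled by dose reduction or switching, and the dose-reduction rule fits the Risks section. One firm conflict remains: the lowest-dose withdrawal rule against the switch. Only hearing aid gain is randomised, both arms are offered the same antidepressants, and participants and treating clinicians are blinded, so drug side effects have little reason to differ by arm. Hearing aid complications prompt an extra audiology visit within the study. This objection stands, which is why the weight here falls on criteria 2 and 3.

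**A missing-data plan may exist elsewhere.** The protocol's reference list includes works on mixed models and informative drop-out, and the full grant application was not available. No supplied text applies those references. The SAP's statement that its model covers all participants is no substitute, since it does not say how an absent Week 12 value is treated.

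**Later ratings would be hard to interpret.** Withdrawn participants receive clinical care and return their devices, so a Week 12 score partly reflects other treatment and no assigned device. This is a genuine choice of estimand. However, the protocol already keeps participants who change antidepressant, so mixed treatment is not new to it.

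**The trial may be over.** The SAP is written in the past tense. If data collection has ended, the lost ratings cannot be recovered and only analysis and reporting remedies remain.

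**Conclusion.** The point holds. Following the plan as written removes participants from the Week 12 analysis because they worsened or, less importantly for the arm comparison, because of side effects or adverse events, with no assessment and no analysis method to offset the loss. The contradiction over participants who tolerate neither drug is real but secondary.

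A reader might go further and conclude that the treatment comparison is biased, or biased towards one arm. The documents do not support that: they give no withdrawal rates by arm. The shift is zero when loss and gap are equal across arms. Under the assumed inputs it is 0.025 to 0.20 residual SD, below the half-width of 0.64 to 0.73. For CGI response, criterion 3 withdrawals are not unknown outcomes, because each has at least two recorded ratings of 6 or 7. The change is worth making because it is cheap and leaves the safety stop intact, not because a large bias has been shown.

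**What to change.** **If participants are still being followed:**
- State that meeting criteria 2 to 4 stops or changes study treatment, while consenting participants still give at least the Week 12 HRSD and CGI and are analysed in their randomised arm.
- Align the lowest-dose rule in the Risks section and criterion 4 with the switch rule: withdraw from study treatment only when continuing is unsafe and cannot be managed by dose reduction or a switch. Which events meet that threshold is for the study clinicians.
- Amend the return term under Hearing aid procedures to say whether someone who stops treatment but gives the Week 12 ratings counts as completing.

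**If data collection has ended:**
- Report withdrawals by arm and reason, and state how missing Week 12 values were handled.
- Count criterion 3 withdrawals as CGI non-responders.
- Add a repeated-measures sensitivity analysis using the Week 2 to 9 HRSD ratings. It assumes that, given the observed ratings and covariates, dropout does not depend on the unseen scores.

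**Cost.** Matching edits to three protocol sections and the consent form, and a few extra ratings. Some Week 12 scores will reflect later clinical treatment or no assigned device. Remote Week 12 ratings are described only in the COVID-19 re-opening text, so elsewhere an in-person visit may be needed. After data collection, the cost is analysis and reporting only.
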